5.4. Prohibited Medications

Any medication, shampoo or hair product known to affect hair growth in AA, AU or AT is prohibited throughout the study period. Subjects who are on a chronic stable dose of finasteride for benign prostatic hypertrophy for greater than 1 year are eligible for enrollment in the study as long as they maintain the same stable dose throughout the study. Treatment with finasteride for alopecia during the study is prohibited.

The following medications and therapies are not permitted during the study:

- Disease Modifying Anti-Rheumatic Drugs (DMARDS), Biologics or immunosuppressants, including but not limited to: anakinra, adalimumab, azathioprine, corticosteroids, cyclosporine, etanercept, infliximab, methotrexate, TNF inhibitors, ustekinumab, and Plaquenil.
- JAK inhibitors (oral or topical) other than ATI-502 Topical Solution.
- Intralesional steroids or platelet rich plasma treatment in the scalp.
- Topical treatments on the scalp with anthralin, bimatoprost, corticosteroids, diphencyprone, diphenylcyclopropenone (DPCP), squaric acid dibutylester (SADBE), minoxidil, pimecrolimus, or tacrolimus.
- Phototherapy (narrow band Ultraviolet B [NB UVB] or broadband therapy).

Date: 09NOV2018, Version 1.0 Page 32 of 80 CONFIDENTAL

Any prohibited medications taken by a subject in violation of the protocol requirements will be documented in the source record and eCRF. Discussion with the Sponsor's Medical Monitor must also take place to determine if the subject's continuation in the study is allowed.

Treatment Compliance 5.5.

The investigator or designee will be responsible for monitoring subject compliance through questioning the subject, reviewing the subject completed compliance record and documenting missed doses, if any, and visual inspection of the study medication bottles (used and unused). Study staff will counsel the subjects, as required to make sure subjects are compliant with study medication dosing.

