- Hair quality assessment including normalization of exclamation point hairs and hair shedding will be described.
- Vellus and Indeterminate scalp hair will be described.
- Non-scalp hair assessments (body and nasal hair) will be described.

Statistical Methods:

Sample Size/ Power Calculations

The planned sample size 80 enrolled is based on an estimated completion rate from study ATI-501-AUAT-201.

Statistical Methods

Subject demographic and baseline characteristics, including medical and alopecia history, prior medications and therapies and physical examination findings will be summarized using descriptive statistics.

Summary descriptive statistics (N, mean, median, SD) by visit will be provided for all safety and efficacy parameters. The Intent to Treat population will be used for all efficacy assessments and the Safety population will be used for all safety assessments. No data imputation will be used.

No inferential analyses are planned. For all efficacy evaluations described below, summary statistics will be provided for all treated subjects pooled, and also for each of two sub-groups of subjects based on the treatment they previously received in study ATI-501-AUAT-201.

Primary Efficacy Analyses

For the primary endpoint, the primary efficacy variable will be the mean relative percent change from the original baseline visit in study ATI-501-AUAT-201 in the SALT score to Visit 6 (Week 24). This represents the percentage of hair regrowth. It will be calculated as the mean of the changes from baseline SALT score to the SALT score at Visit 6 (Week 24), divided by baseline SALT score and expressed as a percentage.

Date: 09NOV2018, Version 1.0 Page 7 of 80 CONFIDENTAL

Secondary Efficacy Analyses

Protocol: ATI-502-AA-203

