ALODEX Score (after SALT) ¹¹	✓	(X) [^]		X	X	X	X	X
Vellus and Indeterminate Hair Assessment	✓	(X) [^]		X	X	X	X	X
Photography (complete scalp)	✓	(X) [^]		X	X	X	X	
Subject instructions ¹²		X	X	X	X	X		
In office study medication application		X						
Dispense study medication ¹³		X	X	X	X	X		
Collect study medication and assess compliance ¹⁴			X	X	X	X	X	
Concomitant therapies	√	(X) [^]	X	X	X	X	X	X
Adverse events	√	(X) [^]	X	X	X	X	X	X

Abbreviations: CR= Clinician Rating; ET= Early termination Visit; SR= Subject Rating

¹Visit 1 will occur on the same day as Visit 9 of study ATI-501-AUAT-201. Visit 9 procedures for study ATI-501-AUAT-201 must be completed prior to initiation of any study related activity for ATI-502-AA-203. Eligible subjects must sign consent prior to first application of topical study medication. The assessments performed for Visit 9 in study ATI-501-AUAT-201 will be entered into the source document and eCRF for Visit 1 in study ATI-502-AA-203. ATI-502-AA-203 enrollment may not be open at the time of a subject's ATI-501-AUAT-201 Visit 9. If this scenario occurs, the subject may be brought back to the clinic prior to their ATI-501-AUAT-201 Visit 10. At this visit, the subject will then be given topical treatment. Assessments marked as (X)^ represent repeat assessments that would need to be performed if the subject cannot enroll directly at Visit 9 (or within 14 calendar days of Visit 9) from study ATI-501-AUAT-201.

²A written, signed ICF must be obtained from each subject prior to performing any study related procedure.

³A physical examination includes: General appearance, examination of the head, eyes, ears, nose and throat, respiratory, cardiovascular, abdominal, extremities, musculoskeletal, lymphatic, skin (other than AA) and neurological assessment.

⁴Vital signs include oral or ear temperature, blood pressure, heart rate, respiration rate.

⁵ For WOCBP, the UPT performed at Visit 9 in study ATI-501-AUAT-201 must be negative prior to study medication application. UPT in WOCBP must also be obtained at Visits 3, 4, 5, 6, and 7 and must be negative for the subject to continue in the study.

⁶ The subject should perform assessments prior to the Investigator assessments. The investigator may assist the subject in locating a Target Patch.

⁷The subject should refer to the Baseline (Visit 2 from ATI-501-AUAT-201 and Visit 1 from ATI-502-AA-203) photographs when assessing the change over time.

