4.3. Subject Withdrawal Criteria

Protocol: ATI-502-AA-203

Subjects will be informed that they are free to withdraw from the study at any time and for any reason. The investigator may remove a subject from the study if, in the investigator's opinion, it is not in the best interest of the subject to continue the study. Examples of other reasons subjects may be discontinued from the study are: a change in compliance with an inclusion or exclusion criterion, occurrence of AEs, occurrence of pregnancy, use of a prohibited therapy or subject is unwilling or refuses to continue with the protocol defined study visits and/or subject withdraws consent (Refer to Section 3.4.1.2 for study medication discontinuation or termination criteria).

In case of premature discontinuation from study participation, all efforts will be made to perform all Week 24 (Visit 6) assessments. The date the subject is withdrawn from the study and the reason for discontinuation must be recorded in the subject's electronic case report forms (eCRFs). All withdrawn subjects with ongoing AEs will be followed until the event has resolved or stabilized, until the subject is referred to the care of a local health care professional, or until a determination of a cause unrelated to the study medication or study procedures is made.

Date: 09NOV2018, Version 1.0 Page 30 of 80

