9.2. Analysis Populations

The Safety analysis population will be comprised of all subjects who received at least one dose of study medication. The Efficacy analysis population will include all subjects who received at least one dose of study medication using observed cases with no imputation for missing data.

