9.4. Efficacy Analyses

Hair regrowth is determined based on both percent scalp hair regrowth (Baseline SALT – Follow-up SALT/Baseline SALT) and change in absolute percent scalp hair loss from baseline (Baseline SALT – Follow-up SALT). A responder is a subject who achieves a SALT50 or SALT75 defined as $\geq 50\%$, $\geq 75\%$ improvement in SALT score from baseline values in the ATI-501-AUAT-201 study. Durability of response will be assessed in subjects who achieved a SALT50 or SALT75 in study ATI-501-AUAT-201. Results will be summarized using descriptive statistics.

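### SALT recorded after a prohibited alopecia therapy has no analysis rule and would be summarised as ATI-502 response; Section 5.4 also does not name scalp laser, photodynamic or device therapy

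*Combined protocol and SAP*

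**What the plan says.** **Conduct.** Section 5.4 lists prohibited therapies, requires any use to be documented, and leaves continuation to a case-by-case decision: "Discussion with the Sponsor's Medical Monitor must also take place to determine if the subject's continuation in the study is allowed". Section 4.3 gives "use of a prohibited therapy or subject is unwilling or refuses to continue" among example reasons for discontinuation, so withdrawal is possible but not mandatory. For those who do leave, "In case of premature discontinuation from study participation, all efforts will be made to perform all Week 24 (Visit 6) assessments"; the Table 3 column for that visit is headed Visit 6 (ET), with the footnote "ET= Early termination Visit". Section 12.4 sends protocol violations to the Medical Monitor and the IRB.

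**Analysis.** Under Section 9.2 the "Efficacy analysis population will include all subjects who received at least one dose of study medication using observed cases". The synopsis names the intent-to-treat population for efficacy and adds "No data imputation will be used" and "No inferential analyses are planned". Section 9.4 defines a responder purely by the size of the SALT improvement, and "Durability of response will be assessed in subjects who achieved a SALT50 or SALT75 in study ATI-501-AUAT-201". No per-protocol population is defined; the term appears only in the abbreviation list.

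**The prohibited list.** The general ban in Section 5.4 covers medications, shampoos and hair products. Its only light-based item is phototherapy, described as narrow-band UVB or broadband. Section 1.1 names photodynamic therapy and lasers among treatments used for extensive disease, and Appendix 1 records PDT, phototherapy and laser as separate prior therapies. Section 5.2 counts energy-based treatments as concomitant therapy, but its condition that efficacy must not be affected is written for medications.

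**The concern.** The study is open-label with no reference therapy, so the descriptive figures are the result. No control arm shows how much regrowth comes from other treatment. If a subject starts an effective alopecia therapy and stays in the study, later SALT values reflect both treatments, yet nothing in Section 9 separates them.

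An additional objective (Section 2.1) is whether ATI-502 maintains or improves earlier regrowth. Section 1.5 reports shedding and substantial loss soon after oral JAK inhibitors are stopped, so subjects coming off ATI-501 who lose hair have a reason to look for something else. That argument does not extend to prior-placebo subjects. Section 1.5 also describes promising case reports with oral tofacitinib and ruxolitinib, so an off-protocol JAK inhibitor could plausibly carry a subject across 50% or 75%. Where the other therapy works, the error favours ATI-502.

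The gap in the prohibited list adds to this. A site could read scalp laser as not prohibited, and the use would then not trigger the review in Section 5.4 at all.

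**Working it through.** The plan states no figure on this point to reproduce. The check is a reading of how values flow into the summaries, followed by simple arithmetic.

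**Which values enter**

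1. *Subject allowed to continue.* SALT is scheduled at Weeks 4, 8, 16, 24 and 28 (Table 3). Sections 9.2, 9.4 and 9.4.1 contain no rule to exclude, censor, reclassify or separately show a value recorded after another therapy. Under an observed-case summary of all dosed subjects, the value enters like any other.
2. *Subject withdrawn.* Section 4.3 seeks the Visit 6 assessments at discontinuation. Visit 6 is scheduled at Day 169 ± 3, and the primary endpoint is at Week 24. The protocol does not say whether an early-termination value is analysed as Week 24. The column heading allows that mapping but does not settle it, so this route is possible, not established.
3. *Durability.* Section 2.2.2 asks for response to be maintained at post-baseline visits and does not say whether scoring is sustained or visit by visit. Take a parent-study responder who falls below 50% at Week 8, starts another therapy and is back above 50% at Week 24. Scored visit by visit, the subject counts as maintained at Week 24. Scored as sustained maintenance, the subject has already failed at Week 8 and nothing is inflated. If the therapy starts before any loss is observed, the subject counts as maintained either way.

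**Size per affected subject**

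Input from the documents: about 80 enrolled (Sections 3.2 and 9.1). Everything else is assumed: the number of affected subjects k, the extra percent regrowth d from the other therapy, and the number of parent-study responders.

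- Responder proportion, for subjects who would otherwise have failed: shift = k/n. At k = 1 and n = 80, 1/80 = 1.25 percentage points.
- Durability, at assumed denominators of 40, 20 and 10: 1/40 = 2.5, 1/20 = 5 and 1/10 = 10 points.
- Primary mean: shift = k × d/n. At k = 1 and n = 80, 25/80 = 0.31, 50/80 = 0.63 and 75/80 = 0.94 points.
- Illustration with k = 4 (5% of 80): 4/80 = 5 points on pooled SALT50, and 4 × 50/80 = 2.5 points on the mean at d = 50.

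**The prohibited list**

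Set Section 5.4 beside Section 1.1 and Appendix 1. Laser and PDT appear in the latter two as alopecia treatments and are absent from Section 5.4. The general ban might reach the photosensitising drug used in PDT; it does not plainly reach a laser or other device. Section 5.2 shows the intent to keep out anything that affects efficacy, but its wording stops at medications.

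**The case against.** The strongest reply is that summarising all observed data, whatever else the subject took, is a legitimate choice for a descriptive open-label extension, and that counting such visits as non-response brings its own bias. That stands. It is why the planned summary should stay and the alternative should be supportive.

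Conduct controls also limit exposure. JAK inhibitors other than ATI-502 are expressly banned, use is documented and discussed with the Medical Monitor, and concomitant therapies are recorded at every visit. These steps make affected visits rarer and identifiable, but they do not say how a recorded value is analysed. Section 1.1 calls the other treatments for extensive disease, including laser and PDT, of unproven efficacy, so their omission from Section 5.4 is a drafting gap with little demonstrated effect on the results.

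Section 9.4.2 defers other parameters to a statistical analysis plan, and Section 10.3 has evaluability determined before lock. A rule could sit there. None is stated in the documents, and the responder and durability measures are defined in the protocol itself.

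A reader might also infer more than the text supports:

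- That Section 9.2 directs values after prohibited therapy to be counted as response. It does not mention prohibited therapy; the effect follows from its general rule together with the silence of Section 9.4.
- That every early-termination value becomes a Week 24 value. The protocol does not say so.
- That durability is inflated whenever another therapy is used. This holds only with visit-by-visit scoring, or when the therapy starts before an observed loss.
- That 1.25 points is a minimum. Enrolment is approximate, so it is only the value at n = 80.

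**Conclusion.** The point holds as a gap in the analysis rules and a smaller gap in the prohibited list. Followed as written, the plan summarises SALT after a prohibited alopecia therapy as ATI-502 response in any subject allowed to continue, and possibly in a withdrawn subject if the early-termination visit is mapped to Week 24.

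The total effect cannot be stated, because the documents give no rate of other-therapy use. The per-subject figures assume that the subject would otherwise have failed. On that basis the effect is about 1.25 points on SALT50 or SALT75 at n = 80, and larger in durability under the scoring conditions above. The effect on the primary mean is small. Since nothing is tested, this is a question of how the summary is read, not of type I error or power. It does not show that the results will be materially biased; it shows that a reader could not tell. It is a worthwhile, inexpensive improvement.

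**What to change.** 1. **Section 5.4.** Add laser, photodynamic and other device or energy-based therapy applied to the scalp or eyebrows to the prohibited list.
2. **Section 9.4.** Keep the all-observed summary as planned. Add a supportive summary of SALT50, SALT75 and durability in which visits on or after the start of any therapy prohibited by Section 5.4, scalp or systemic, count as non-response or not maintained. Include scalp corticosteroids whatever the reason for use. Show mean SALT change with and without those visits.
3. **Listing.** List every affected subject with the therapy, its dates and the reason for use. Confirm that the concomitant-therapy eCRF captures start date, stop date and reason, since the documents do not list its fields.
4. **Exemption.** If brief systemic steroid courses for an unrelated illness are to be exempt, fix the limit before database lock. Steroids permitted by Section 5.2 and stable finasteride for benign prostatic hypertrophy are not prohibited and need no exemption.

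The supportive rule changes response status only and fills in no SALT value, so it is compatible with the no-imputation statement.

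Cost: one line in Section 5.4, a few sentences in Section 9.4, one programming flag, one table and one listing, built on data already collected at each visit. The drawback is that some subjects with true ATI-502 response may be counted as failures in the supportive summary; the all-observed summary beside it shows how much that matters.

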5.6. Blinding

This is an open-label study.

Protocol: ATI-502-AA-203

Date: 09NOV2018, Version 1.0 Page 33 of 80 CONFIDENTAL

6. STUDY MEDICATION MATERIALS AND MANAGEMENT

6.1. Study Medication

Protocol: ATI-502-AA-203

The study medication for this study is ATI-502 Topical Solution, 0.46%. The study medication is formulated as a thin clear solution. The inactive ingredients include: water, transcutol P, propylene glycol, PEG400, dimethyl sulfoxide (DMSO), kolliphor CS 20, benzyl alcohol, poloxamer 188, and povidone K30.

Table 4: Investigational Product

STUDY MEDICATION INFORMATION					
Study medication name	ATI-502 Topical Solution				
Dosage Strength	0.46%				
Manufacturer	PMRS, Horsham, PA				
Pharmaceutical Form	Topical Solution				
Container	Amber Glass Bottle, 120 mL (100 mL fill) with screw cap				
Storage Conditions	59°F to 77°F (15°C to 25°C)				
Dose regimen					
Route	Topical to the scalp, and if applicable, eyebrows				
Frequency	Twice-daily				
Duration of administration	24 weeks				
Other supplies	Disposable, single-use droppers, and applicators will be				
	provided.				

6.2. Packaging and Labeling

The study medication must be used by the study subjects only. The study medication will be supplied in amber glass 120 mL bottles with each bottle packaged in a carton. Disposable droppers with 1 mL calibration mark and applicators will be provided Each carton and bottle will be labeled with a single panel label.

Investigational site staff will explain the administration of study medication to subjects. Study medication will be provided by Aclaris Therapeutics, Inc. and labeled according to regulations as detailed in the Pharmacy Manual.

6.3. Study Medication Storage

Study medications must be stored in a secure area with limited access under appropriately controlled and monitored storage conditions. Study medication should be stored at controlled room temperature $59^{\circ}F - 77^{\circ}F$ ($15^{\circ}C - 25^{\circ}C$). Subjects will be instructed to store the study medication in the carton at room temperature, away from heat, moisture, direct light, and to keep it from freezing and out of the reach of children.

6.4. Study Medication Accountability and Disposal

The Principal Investigator or designee is responsible for ensuring accountability for the investigational agent, including reconciliation of medications and maintenance of medication

Date: 09NOV2018, Version 1.0 Page 34 of 80 CONFIDENTAL

records. Upon receipt of study medication, the clinical site will check for accurate delivery and acknowledge receipt by signing (or initialing) and dating the documentation provided. A copy of this document will be submitted to Aclaris Therapeutics, Inc. (or designee) by facsimile or e-mail (scanned copy) and the original will be maintained in the study file. In addition, an accurate study medication disposition record will be kept, specifying the amount dispensed for each subject and the date of dispensing. This inventory record will be available for inspection at any time. At the completion of the study, the original inventory record will be available for review by Aclaris Therapeutics, Inc. upon request. Final medication accountability will be performed by the study monitor at the completion of the study and all used and unused study medication bottles will be disposed of as detailed in the Pharmacy Manual.

Protocol: ATI-502-AA-203

Date: 09NOV2018, Version 1.0 Page 35 of 80 CONFIDENTAL

7. ASSESSMENT OF EFFICACY

Protocol: ATI-502-AA-203

Note that all subject assessments should be performed in the order detailed in Table 5 prior to any investigator assessments. For the purposes of the ATI-502-AA-203 study, subjects will retain their original disease classification (AA, AT, or AU) from the ATI-501-AUAT-201 study. For subjects classified with AA (30%-95% scalp hair loss at Baseline in study ATI-501-AUAT-201), the investigator may assist the subject in determining the location of the target patch by showing him/her baseline photography of the original target patch from the ATI-501-AUAT-201 study. Investigators should not review the subject's completed assessments prior to completing the investigator assessments. The investigator should perform the assessments in the order detailed in Table 6. Detailed instructions for completing the subject and investigator assessments will be provided to the investigational center prior to the initiation of subject enrollment.

7.1. Subject Reported Outcome Assessments

The subject will complete the assessments (questionnaires) in the order detailed in Table 5. The subject must sign/initial and date the completed questionnaire to indicate he/she performed the assessment as instructed. The staff member administering the questionnaires must document proper completion of the assessments in the subject's source notes.

Table 5: Subject Assessments

Order	Subjects with Patchy AA (30% – 95% scalp hair loss at Baseline in study ATI-501-AUAT- 201)	Subjects with AU or AT (>95% scalp hair loss at Baseline in study ATI-501-AUAT-201)			
1.	Alopecia Scalp Appearance Assessment for Patchy AA: Subject Rating (ASAA- AAP: SR) Appendix 2	opecia Scalp Appearance Assessment for Γ/AU: Subject Rating (ASAA-AT/AU: SR) opendix 8			
2.	Alopecia Facial Hair Appearance Assessment: Subject Rating (AFHA: SR) Appendix 3				
3.	Subject Global Impression of Severity for Patchy AA (SGIS-AAP) Appendix 4	Subject Global Impression of Severity for AT/AU (SGIS-AT/AU) Appendix 9			
4.	Alopecia Impact Assessment (AIA) Appendix 5				
5.	Subject Global Impression of Change (SGIC)* Appendix 12				
6.	Subject Global Impression of Treatment Satisfaction for Patchy AA (SGITS- AAP) Appendix 6	Subject Global Impression of Treatment Satisfaction for AT/AU (SGITS-AT/AU) Appendix 10			
7.	Subject Global Satisfaction with Hair Quality (SGSHQ-AAP) Appendix 7	Subject Global Satisfaction with Hair Quality (SGSHQ_AT/AU) Appendix 11			

^{*}Only assessed at final study treatment visit

